## LY3209590 Dose Adjustment Based on Median FBG

(-) = decrease dose; (+) = increase dose

#### 6.1.5. Insulin degludec Dose Initiation and Modification

In this section, dosing instructions for insulin degludec are provided for

- dose initiation at Visit 3 (Week 0), and
- administration of the daily dose at Visit 4 (Week 1) and subsequent dosing/dose adjustments throughout the treatment period.

Note: The first dose is administered by site personnel; subsequent doses are self-administered.

# Visit 3 – (Week 0): Randomization Visit Insulin Degludec Dose Determination from Equivalent of Prestudy Insulin Dose

Follow instructions in the Equivalent Dose of Insulin Degludec table below, to calculate the equivalent dose of insulin degludec to be administered by the participant once daily.

**Note:** If a participant is on NPH twice-daily or U300 glargine, the prestudy basal insulin dose should be reduced by 20% when determining the once-daily dose of insulin degludec to initiate in the study.

#### **Equivalent Dose of Insulin Degludec**

Step	Action	Example Participant C Prestudy insulin: glargine, U100 20 units once-daily	Example Participant D Prestudy insulin: NPH, 10 units twice- daily
1.	Determine usual prior daily basal dose from lead-in period	20 units/day	10 units $\times$ 2 = 20 units/day
2.	Determine daily dose of insulin degludec	20 units/day	$20 \text{ units} - [20 \times 0.2] \text{ units} = 20 \text{ units} - 4$ $\text{units} = 16 \text{ units/day}$

## Visit 4 (Week 1) to Visit 37 (Week 78)

If the participant experienced any documented hypoglycemia (BG  $\leq$ 70 mg/dL [3.9 mmol/L]) in the previous week, the dose should not be increased.

If the participant experienced hypoglycemia in the previous week that met dose reduction criterion, decrease the daily dose as described in the Hypoglycemia Dose Reduction Criteria for Insulin Degludec table below.

Hypoglycemia Dose Reduction Criteria	Unit Dose Decrease
Based on BG Values	
$\geq$ 3 episodes of $\leq$ 70 mg/dL ( $\leq$ 3.9 mmol/L)	
$\geq$ 1 nocturnal episode $\leq$ 70 mg/dL (3.9 mmol/L)	2–6 units a
$\geq$ 1 episode <54 mg/dL (3.0 mmol/L)	2-0 units
Any confirmed severe hypoglycemia	

## Hypoglycemia Dose Reduction Criteria for Insulin Degludec

a Dose reductions of 2 or 4 units may occur every 3 days to achieve a gradual weekly reduction of 6 units as clinically indicated.

If hypoglycemia dose reduction criteria are not met, use the median FBG from the previous week to obtain the dose adjustment from the titration algorithm in the Insulin Degludec Dose Adjustment table below. If the median FBG is within the target range from 80 to 120 mg/dL (4.4 to 6.6 mmol/L), no change would be made to the dose from the previous week.

Median FBG		Insulin Degludec Dose Adjustment	
mg/dL	mmol/L	units	
<80	<4.4	(-) 3 units (decrease)	
80-120	4.4-6.6	No change	
121-140	6.7-7.7	(+) 3 units (increase)	
>140	>7.7	(+) 6 units (increase)	

## **Insulin Degludec Dose Adjustment**

## 6.1.6. Management of Hypoglycemia

At Visit 2 (Week -2), participants who have not screen failed will be trained by authorized site personnel about signs and symptoms of hypoglycemia and how to treat hypoglycemia and how to document episodes in the e-diary.

This section provides guidance on management of episodes of hypoglycemic events. For effective implementation of measures described here, it is important that participants, and their caregivers, if applicable, be well-educated about the signs and symptoms of hypoglycemia (for example, intense hunger, sweating, tremor, restlessness, irritability, depression, headaches, disturbed sleep, or transient neurological disorders) and its treatment. Participants should be instructed how to treat all levels of hypoglycemia and that if they experience an event of severe hypoglycemia, they should notify the site as soon as possible after the event has been successfully treated (see Section 8.3.3).

The allowable non-insulin antihyperglycemic medications are not insulin secretagogues; therefore, clinically relevant increases in the risk of hypoglycemia due to these medications are not expected. To date, effects of LY3209590 on hypoglycemia are not different as compared to other basal insulins, so the management of hypoglycemia is similar for the study participants in both treatment groups.

Study participants will be instructed to use standard precautions prior to and during exercise.

Study participants will be instructed to check their BG, when they experience signs and symptoms suggestive of hypoglycemia, and to administer appropriate treatment for when BG

 $\leq$ 70 mg/dL (3.9 mmol/L). They will be instructed to recheck BG levels 15 minutes following treatment of hypoglycemia and repeat treatment and BG recheck after another 15 minutes until the BG level has returned to the target range of 80-120 mg/dL (4.4-6.6 mmol/L) (CDC 2021). Instructions will be provided for clinical management of participants who experience frequent or repeated hypoglycemia. As necessary, additional instruction/education may be provided to participants by investigative staff, including increased BG monitoring, treatment adjustments, or other approaches (for example, behavioral interventions and lifestyle modification) to mitigate hypoglycemia frequency or severity.

Investigators should prescribe glucagon to participants, and family members, housemates, or support care providers should be educated about glucagon administration.

In cases where a participant experiences hypoglycemia as described above, to confirm the increased risk, the study sites must ensure that the participant has been fully compliant with the assigned therapeutic regimen and ensure that there is no evidence of other possible causes of hypoglycemia, for example, omission of meal, inadequate meal, and unexpected increase in exercise.

Participants experiencing severe hypoglycemia at any time should be evaluated by the investigator to determine if criteria are met for adjustment of the basal insulin based on the dosing algorithm (Section 6.1) first and then if needed, consider adjusting current concomitant antihyperglycemic medications. If discontinuation of IP is required for hypoglycemia that is refractory to decreasing the dose of non-insulin anti-hyperglycemic medications or other interventions or there are other safety concerns, the investigator should notify the sponsor and complete an AE form, indicating discontinuation of IP related to hypoglycemia. The investigator and the Lilly research scientist or physician will determine alternative treatment (if applicable) and whether continued participation in study and safety follow-up while not on IP is appropriate.

## 6.2. Preparation, Handling, Storage, and Accountability

The investigator or designee must confirm appropriate storage conditions have been maintained during transit for all study intervention received, and any discrepancies are reported and resolved before use of the study intervention.

Only participants enrolled in the study may receive study intervention. Only authorized study personnel may supply, prepare, or administer study intervention. All study intervention must be stored in a secure, environmentally controlled, and monitored (manual or automated) area in accordance with the labeled storage conditions with access limited to the investigator and authorized study personnel.

The investigator or authorized study personnel are responsible for study intervention accountability, reconciliation, and record maintenance (that is, receipt, reconciliation, and final disposition records).

Further guidance and information for the final disposition of unused study interventions are provided in the Pharmacy Manual.

In-use storage conditions must be followed according to the Instructions for Use provided by the sponsor. Study participants will be trained on the proper storage and handling of the study

intervention. Study participants will be provided with cartons containing the required number of pens at clinic visits as shown in the SoA (Section 1.3).

# 6.3. Measures to Minimize Bias: Randomization and Blinding

This is an open-label study. Investigators and participants will be unblinded to the assigned treatment groups. Assignment to treatment groups will be determined by an IWRS. Participants will be randomly assigned to 1 of the 2 treatment groups in 2:1 ratio (LY3209590:insulin degludec) at Visit 3 (Week 0). Stratification will be by country, HbA1c stratum at Visit 1 (Week -3) (<8.0%,  $\geq$ 8.0%), and the type of basal insulin regimen at randomization (a. typical once-daily basal insulin; b. U-300 or NPH BID regimens which need reduction in total daily dose (TDD)/conversion to equivalent dose for typical once-daily U-100 basal insulin regimen).

All study IP will be assigned by IWRS. Site personnel will confirm that they have located and are dispensing the correct IP by entering a confirmation number found on the IP label into the IWRS.

The Lilly study team members who are closely involved in data interpretation and analysis planning will remain blinded throughout the course of the trial; only a minimum number of Lilly personnel will see the randomization table and treatment assignments before the study is complete. The investigator should make every effort to preserve the blinding when contacting the Lilly study team members, including the Lilly clinical research physician or scientist.

Interim analyses will be conducted under the auspices of an external DMC. Only the external statisticians from the SAC will have access to the unblinded data that are presented to the DMC. The SAC and members of the DMC will abide by the principles and responsibilities described in the DMC charter, which include all unblinded information confidential until the planned unblinding of the trial.

An early PK/PD unblinded transfer may also be conducted. Only a small group of personnel can be unblinded to the data for the potential PK/PD analysis and must keep information confidential until the planned unblinding of the trial.

# 6.4. Study Intervention Compliance

The investigator or trained designee will assess the treatment (LY3209590 or insulin degludec) compliance at each contact (visit or phone contact) based on review of the participant glycemic control, e-diary completion, and adherence to prescribed dose and study procedures.

Study participants considered to be poorly compliant with their medications and/or study procedures (for example, missed visits or specific diagnostic tests) will be retrained as needed by designated site personnel.

# 6.5. Dose Modification

Dosing will be individualized based on FBG and the sponsor provided algorithm for both study drugs (LY3209590 or insulin degludec) as mentioned in Sections 6.1.4 and 6.1.5. In particular, the dose will be reduced as specified if hypoglycemia criteria are met (See Section 6.1).

## 6.6. Continued Access to Study Intervention after the End of the Study

The sponsor will not provide participants with ongoing supplies of study medication after they have completed the study treatment period or permanently discontinued the study IP.

## 6.7. Treatment of Overdose

Study intervention overdose (dangerously large amount of insulin compared to the protocolprescribed dose) will be reported as per Section 10.3.1. In the event of an overdose, refer to the IB for LY3209590 or product label for insulin degludec depending on the participant treatment assignment.

In the event of an overdose, the investigator/treating physician should

- contact the Lilly-designated medical monitor (for example, CRP/CRS) immediately.
- evaluate the participant to determine, in consultation with the Lilly-designated medical monitor, whether study intervention should be interrupted or whether the dose should be reduced
- closely monitor the participant for any AE/SAE and laboratory abnormalities until study intervention no longer has a clinical effect, and
- if the participant is assigned to LY3209590, a plasma sample for PK analysis may be obtained.

## 6.8. Concomitant Therapy

Study participants will be permitted to use concomitant medications that they require during the study, except excluded medications described in Section 5.2 (Exclusion Criteria) and the table below.

Investigative site staff will inform study participants that they must consult with the investigator or a designated site staff member when prescribed any new medications that may substantially affect glycemic values during the study, except when initiated for treatment of medical emergencies. Any additional medication initiated during the study (including OTC drugs, such as aspirin) must be documented in the CRF with the name of the drug and date(s) of administration. In addition, for permitted concomitant non-insulin antihyperglycemic medications, the dosage will also be documented and collected.

Non-study medications taken by study participants who are screened but not randomly assigned will not be reported to Lilly unless an SAE or AE occurs that the investigator believes may have been caused by a study procedure.

This table provides a summary of criteria for use of concomitant medications during the study.

Drug Class	Use during Screening/ Lead-In	Conditions for Use after Randomization			
		During Treatment Period	Acute Therapy	Rescue Therapy	During Safety Follow- Up Period
Drugs with approved weight loss indication a	Y	Y	Ν	N/A	N
Systemic glucocorticoid therapy b	Ν	Ν	Y°	N/A	N
Antihyperglycemia	Medications				
GLP-1 RAs	Y d	$Y^d$	N/A	Y	Y
DPP-4 inhibitors	$\mathbf{Y}^{\mathrm{d}}$	$\mathbf{Y}^{\mathrm{d}}$	N/A	Y	Y
SGLT2 inhibitors	$\mathbf{Y}^{\mathrm{d}}$	$\mathbf{Y}^{\mathrm{d}}$	N/A	Y	Y
Non-study basal insulins	Y d	(allowed only if study basal insulin is discontinued)	(allowed only if study basal insulin is temporarily discontinued)	See note	Y
Insulin mixtures	N	N	(allowed only if study basal insulin is discontinued)	See note	Y
Prandial insulin	Ν	Ν	Y	Y	Y
Meglitinides	Ν	Ν	N	Ν	Y
Alpha-glucosidase inhibitors	Y d	Y d	N/A	Y	Y
Sulfonylureas	Ν	Ν	N/A	Ν	Y
Thiazolidinediones	Ν	Ν	N/A	Ν	Y
Metformin e	Y d	Y d	N/A	Y f	Y

## **Criteria for Use of Concomitant Medications**

Abbreviations: DPP-4 = dipeptidyl peptidase-4; GLP-1 RA = glucagon-like peptide-1 receptor agonist; N = no; N/A = not applicable; SGLT2 = sodium-glucose cotransporter 2; Y = Yes.

a Participants should not initiate, or change the dose of, any weight loss medication for any reason after screening. Continued use is allowed during study lead-in and treatment period if on stable therapy 90 days prior to screening. These include, but not limited to, liraglutide 3.0 mg, orlistat, sibutramine, mazindol, phentermine, lorcaserin, phentermine/topiramate combination, naltrexone/bupropion, semaglutide injection 2.4 mg, or similar other body weight loss medications, including OTC medications, for example, orlistat 60 mg capsules.

- b Does not apply to topical, intraocular, intranasal, intra-articular, or inhaled preparations.
- c Acute therapy = treatment for up to 14 days.
- d Continued use is allowed during study lead-in and treatment period if on stable therapy 90 days prior to screening.

- e Switching metformin manufacturers is allowed if the dosage is the same. Changing to a metformin formulation with a different action profile (that is, from short-acting to long-acting metformin) is not permitted.
- f For rescue therapy, concomitant antihyperglycemic medication doses may be increased if the dose is below maximum approved dose per country-specific label.

Note: Participants who require a non-study basal insulin or insulin mixture as rescue therapy must discontinue study basal insulin therapy (LY3209590 or insulin degludec). The participant will remain in the study and follow procedures for the remaining study visits.

#### 6.8.1. Rescue Therapy for Management of Participants with Severe / Persistent Hyperglycemia during the Treatment Period

Participants in this clinical trial will be treated with basal insulin (LY3209590 or insulin degludec) that will be titrated to achieve FBG levels at 80-120 mg/dL (4.4- 6.6 mmol/L). They will also be instructed to regularly perform SMBG (predominantly FBG but investigator may instruct the participant to check BG at other timepoints to better inform dose adjustments and manage other aspects of clinical care). An additional antihyperglycemic medication should be considered if a participant develops severe, persistent hyperglycemia after randomization, based on meeting one of the following criteria and in the absence of intercurrent cause of the hyperglycemia (investigators should first confirm that the participant is fully compliant with the assigned therapeutic regimen and that they do not have an acute condition causing severe hyperglycemia):

- average of FBG over 2-week period >270 mg/dL (15 mmol/L) from Visit 11 (Week 8) to Visit 15 (Week 12)
- average of FBG over 2-week period >240 mg/dL (13 mmol/L) from Visit 15 (Week 12) to Visit 22 (Week 26), and
- average of FBG over 2-week period >200 mg/dL (11 mmol/L) from Visit 22 (Week 26) to Visit 37 (Week 78).

The investigator should ensure that the participant met the criteria for severe or persistent hyperglycemia before initiating rescue medicine and document this in the source files.

Rescue therapy for consideration will commence with dose optimization of the participant's concomitant antihyperglycemic medications and/or addition of allowed concomitant antihyperglycemic medications if applicable so the participant is on up to 3 antihyperglycemic medications at effective doses before considering insulin rescue therapy. If severe, persistent hyperglycemia is not improving and there is participant compliance with the assigned therapeutic regimen and optimization of other/concomitant glucose-lowering agents, the addition of prandial insulin may be considered.

At Visit 22 (Week 26) or after, addition of prandial insulin may also be considered for rescue therapy without changing the participant's concomitant glucose-lowering medications if it is apparent that overbasalization is a problem. Situations that may suggest potential overbasalization include persistent elevated FBG due to elevated post-dinner BG, or elevated BGs at other times of the day (for example, following or in-between meals) while FBG is relatively well controlled or accompanied by hypoglycemia that is unexplained by activity, diet, or other factors.

Participants who receive rescue therapy for hyperglycemia management should also continue administering IP for the remaining period in the trial.

Participants who require a non-study basal insulin or insulin mixture as rescue therapy must discontinue study basal insulin therapy (LY3209590 or insulin degludec). The participant will remain in the study and follow procedures for the remaining study visits.

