## Justification for the LY3209590 single loading dose

Following a once-weekly subcutaneous administration of LY3209590, the time to reach steadystate PK without a loading dose is estimated to be between 8 and 10 weeks based on the long half-life of LY3209590. With a loading dose, the estimated time to reach steady state is within 2-3-weeks. Participants randomly assigned to LY3209590 with median FBG >120 mg/dL (6.6 mmol/L) will receive a single loading dose of LY3209590 that is 3-times the weekly dose calculated from their previous daily basal insulin dose multiplied by 7 (see Section 6.1). This strategy was designed to minimize loss of glycemic control when transitioning from the shorter duration once-daily basal insulins to a weekly insulin. This approach is supported by findings in the multiple-ascending dose Study BDCB, the Phase 2 Study BDCM, and model-based simulations.

For participants who are entering the study in good glycemic control

(FBG  $\leq 120 \text{ mg/dL}$  [6.6 mmol/L]), a loading dose is not recommended. In such cases, treatment should be started using the weekly dose calculated from their previous daily basal insulin dose multiplied by 7 (see Section 6.1).

Directions for conversion of the prior daily basal insulin dose to the LY3209590 weekly dose are described in Section 6.1. The method to calculate the one-time loading dose and the titration rules to be used beginning at Visit 5 (Week 2) are also described in Section 6.1.

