## Visit 3 – (Week 0): Randomization Visit

Determine the median FBG from the week prior to randomization (Visit 3 [Week 0])

Follow instructions in the LY3209590 Loading Dose Calculation table below for participants with FBG >120 mg/dL (6.6 mmol/L)

Follow instructions in the LY3209590 Starting Weekly Dose Calculation table below for participants with FBG  $\leq 120 \text{ mg/dL}$  (6.6 mmol/L)

**Note:** If a participant is on NPH twice-daily or U300 glargine, the prestudy basal insulin dose should be reduced by 20% when determining Usual Daily Dose of the prestudy basal insulin before calculating the Starting Weekly Dose.

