# Source documents at alternate locations

Source documents generated at a location other than the study site should be part of the investigator's source documentation and should be transferred to the site in a secure and timely manner.

Term	Definition	
abuse	Use of a study intervention for recreational purposes or to maintain an addiction or dependence	
ADA	antidrug antibody	
AE	adverse event	
ALT	alanine aminotransferase	
ALP	alkaline phosphatase	
AST	aspartate aminotransferase	
Blinding/masking	A single-blind study is one in which the investigator and/or his staff are aware of the treatment, but the participant is not, or vice versa, or when the sponsor is aware of the treatment, but the investigator and/his staff and the participant are not.	
	A double-blind study is one in which neither the participant nor any of the investigator or sponsor staff who are involved in the treatment or clinical evaluation of the subjects are aware of the treatment received.	
BG	blood glucose	
CGM	continuous glucose monitoring; can refer to study procedure or analysis of representative CGM-derived variables including but not limited to:	
	
 
time in range from 70 to 180 mg/dL (3.9 to 10 mmol/L) and 70 to 140 mg/dL (3.9 to 7.7 mmol/L)
 
time below range from ≥54 mg/dL (3 mmol/L) to <70 mg/dL (3.9 mmol/L), <70 mg/dl (3.9 mmol/L), and <54 mg/dL (3 mmol/L)
 
time above range from >180 mg/dL (10 mmol/L) to ≤250 mg/dL (13.9 mmol/L) and >250 mg/dL (13.9 mmol/L)
 
daily average glucose
 
glucose management indicator
 
between- and within-day glucose variability
 
low blood glucose index; high blood glucose index; blood glucose risk indicator; and
 
ambulatory glucose profiles with interquartile ranges.
 
	
CIOMS	Council for International Organizations of Medical Sciences	
BGM	blood glucose meter	
Companion diagnostic	An in vitro diagnostic device (assay or test) that provides information that is essential for the safe and effective use of a corresponding therapeutic product	
complaint	A complaint is any written, electronic, or oral communication that alleges deficiencies related to the identity, quality, purity, durability, reliability, safety or effectiveness, or performance of a drug or drug delivery system.	

**10.8.** Appendix 8: Abbreviations and Definitions

Compliance	Adherence to all study-related, good clinical practice (GCP), and applicable regulatory requirements.
CI	confidence interval

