6.6.1. Glucose in Target Ranges, Hypoglycemia or Hyperglycemia

The following variables of time in range, hypoglycemia, hyperglycemia during each CGM session will be derived:

- Percentage and Duration (in minutes) of time per day where glucose values are within a hypoglycemic range (defined as <54 mg/dL [3.0 mmol/L]) during the nighttime period (defined as midnight to 0600 hours), the daytime period (defined as 0600 hours to 2400 hours) and a 24-hour period.
- Percentage and Duration (in minutes) of time per day where glucose values are within a hypoglycemic range (defined as <70 mg/dL [3.9 mmol/L] and ≥54 mg/dL [3.0 mmol/L]) during the nighttime period, the daytime period and a 24-hour period.
- Percentage and Duration (in minutes) of time per day where glucose values are within a hypoglycemic range (defined as <70 mg/dL [3.9 mmol/L]) during the nighttime period, the daytime period and a 24-hour period.
- Percentage and Duration (in minutes) of time per day glucose values are within a hyperglycemic range (defined as >180 mg/dL [10.0 mmol/L] and ≤ 250 mg/dL [13.9 mmol/L]) during the nighttime period, the daytime period and a 24-hour period.
- Percentage and Duration (in minutes) of time per day glucose values are within a hyperglycemic range (defined as >250 mg/dL [13.9 mmol/L]) during the nighttime period, the daytime period and a 24-hour period.
- Percentage and Duration (in minutes) of time per day glucose values are within a hyperglycemic range (defined as >180 mg/dL [10.0 mmol/L]) during the nighttime period, the daytime period and a 24-hour period.
- Percentage and Duration (in minutes) of time per day glucose values are within a glycemia range (defined as between 70 mg/dL and 180 mg/dL [3.9 and 10.0 mmol/L]) inclusive during the nighttime period, the daytime period and a 24-hour period.
- Percentage and Duration (in minutes) of time per day glucose values are within a glycemia range (defined as between 70 mg/dL and 140 mg/dL [3.9 and 7.8 mmol/L] inclusive) during the nighttime period, the daytime period and a 24-hour period.

The percentage of time within a glucose range (target, hypoglycemia or hyperglycemia ranges) will be calculated as the number of observations within the specified range divided by the number of observations in the time interval (for example, 24-hour period). The average percentage of time among valid CGM days for the corresponding time interval during each CGM session will be used in the analysis.

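### Two rescue criteria in Protocol 6.8.1 print mmol/L equivalents that are lower cut-offs than their mg/dL values (240/13 and 200/11), and no governing unit is named

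*Protocol*

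**What the plan says.** Protocol 6.8.1 lists three fasting blood glucose (FBG) criteria for considering rescue, each in two units:

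- Weeks 8 to 12: "average of FBG over 2-week period >270 mg/dL (15 mmol/L"
- Weeks 12 to 26: "average of FBG over 2-week period >240 mg/dL (13 mmol/L) from Visit 15 (Week 12) to Visit 22 (Week 26"
- Weeks 26 to 78: "average of FBG over 2-week period >200 mg/dL (11 mmol/L) from Visit 22 (Week 26) to Visit 37 (Week 78"

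The investigator must make sure that the criterion was met and document this before starting rescue. SAP Section 3 cuts EAS2 data at the earlier of the first rescue date and the last study dose plus an arm-specific number of days.

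Protocol 4.3 and 6.1.3 to 6.1.5 print 120 mg/dL as 6.6 mmol/L for the loading dose ("LY3209590 with median FBG >120 mg/dL (6.6 mmol/L) will receive a single loading dose") and for the upper end of the titration target. Section 6.8.5.1 uses the same pair for starting non-study basal insulin after LY3209590. The titration tables of both arms print 121–140 mg/dL as 6.7–7.7 mmol/L and the top row as >140 and >7.7.

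The CGM definition in Protocol 10.8 has "70 to 140 mg/dL (3.9 to 7.7 mmol/L", while SAP 6.6.1 gives the same range as "3.9 and 7.8 mmol/L] inclusive". The amendment b summary describes the mmol/L figures as corresponding values added for clarity. Neither document says which unit governs or which unit the meter, e-diary or portal displays.

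**The concern.** A threshold printed in two units should be one threshold. Where the figures differ, a value between them satisfies the rule in one unit and fails it in the other. Here the rules are treatment decisions, and one of them (rescue) is also an intercurrent event in the efficacy estimand. The requirement to document that the rescue criterion was met presupposes a single criterion. SAP Appendix 2, which counts prescribed doses that differ from the algorithm dose, likewise presupposes one algorithm answer for each glucose value.

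**Working it through.** **Conversion factor.** The documents state none. Their own pairs 270/15 and 180/10.0 imply k = 18.0 mg/dL per mmol/L. I assume k between 18.0 and 18.0182; the conclusions hold across that range.

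**Each pair.** Exact mmol/L = mg/dL ÷ k. Printed value in mg/dL = printed mmol/L × k. Gap = mg/dL value minus the latter.

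| Printed pair | Exact mmol/L | Printed mmol/L back in mg/dL | Gap, mg/dL |
|---|---|---|---|
| 270 / 15 | 14.99–15.00 | 270.0–270.3 | −0.3 to 0 |
| 240 / 13 | 13.32–13.33 | 234.0–234.2 | 5.8–6.0 |
| 200 / 11 | 11.10–11.11 | 198.0–198.2 | 1.8–2.0 |
| 120 / 6.6 | 6.66–6.67 | 118.8–118.9 | 1.1–1.2 |
| 140 / 7.7 | 7.77–7.78 | 138.6–138.7 | 1.3–1.4 |
| 140 / 7.8 (SAP) | 7.77–7.78 | 140.4–140.5 | −0.5 to −0.4 |

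The first row reproduces the plan's own figure. The values 13 and 11 arise only by rounding to a whole number. The values 6.6 and 7.7 arise only by truncation, whereas 70/3.9 and 250/13.9 in the same protocol are rounded.

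**Rescue bands.** A 2-week mean of about 234 to 240 mg/dL (Weeks 12–26) or 198 to 200 mg/dL (Weeks 26–78) meets the mmol/L criterion but not the mg/dL one.

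**One-decimal pairs.** A median of exactly 120 mg/dL shows as 6.7 mmol/L. In mg/dL it means no loading dose and no titration change. In mmol/L it exceeds 6.6, so it falls under the loading-dose instruction for "participants with FBG >120 mg/dL (6.6 mmol/L" and in the 6.7–7.7 titration row. Exactly 140 mg/dL shows as 7.8 and moves from the 121–140 row to the >7.7 row. The loading dose and the choice of titration column exist in the LY3209590 arm only; the titration target and rows exist in both arms.

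**Can one decimal avoid this?** No:

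- 120 and 121 mg/dL both show as 6.7, and 140 and 141 both show as 7.8, so any one-decimal cut-off misplaces one of each pair.
- The correctly rounded 80/4.4 does the same. 79 ÷ 18 = 4.39 shows as 4.4, which is a decrease in mg/dL but no change in mmol/L.
- So does 70/3.9. 71 ÷ 18 = 3.94 shows as 3.9, which meets ≤3.9 although 71 is not ≤70.

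**Size of the rescue effect.** Assumption: 2-week mean FBG is normal with mean 140–150 and SD 30–40 mg/dL. The documents give no such figures. With k = 18.0156, the added proportion is P(FBG > 13k) − P(FBG > 240) in Weeks 12–26, and P(FBG > 11k) − P(FBG > 200) in Weeks 26–78.

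| Mean, SD | >240 | >13 mmol/L | Added | >200 | >11 mmol/L | Added |
|---|---|---|---|---|---|---|
| 140, 30 | 0.04% | 0.08% | 0.04 pts | 2.28% | 2.62% | 0.35 pts |
| 140, 40 | 0.62% | 0.93% | 0.31 pts | 6.68% | 7.29% | 0.61 pts |
| 150, 30 | 0.13% | 0.25% | 0.12 pts | 4.78% | 5.42% | 0.64 pts |
| 150, 40 | 1.22% | 1.76% | 0.54 pts | 10.56% | 11.42% | 0.86 pts |

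With k = 18.0 the largest values become 0.56 and 0.94 points. If all 939 participants were judged in mmol/L, the upper ends at k = 18.0156 are 939 × 0.0054 ≈ 5 and 939 × 0.0086 ≈ 8 participants.

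**The case against.** The strongest reply is that this is ordinary rounding. The mg/dL value leads everywhere and mmol/L stands in brackets as an equivalent. Nothing shows that any site, meter or portal works in mmol/L. Rescue is to be considered, not triggered, after compliance is confirmed and acute causes are excluded, and investigators may depart from the dose algorithm with a documented reason.

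Much of this stands. For 120/6.6 and 140/7.7 the boundary problem comes with one-decimal values, and printing 6.7 and 7.8 would only move it to 121 and 141 mg/dL. It does not dispose of 240/13. That gap of about 6 mg/dL is far wider than display rounding, and the same list shows the conversion done correctly.

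Two stronger readings are tempting. One is that all four pairs are errors of the same kind. The 80/4.4 and 70/3.9 pairs, which are correctly rounded, show the same one-unit effect, so that does not follow. The other is that participants are dosed or rescued differently by country. The documents never say which unit any country uses, so that remains a possibility only. A relative figure, such as 1.4 to 2.0 times as many participants qualifying in Weeks 12 to 26, would also mislead, because the underlying proportions are below 2%.

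The 7.7 against 7.8 disagreement concerns a CGM analysis range and drives no treatment decision.

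**Conclusion.** The two rescue pairs in 6.8.1 are inconsistent within the protocol, and nothing says which figure prevails. The other pairs are 1 to 2 mg/dL boundary effects that a governing unit would settle. For the loading dose and titration column they touch the LY3209590 arm only.

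The expected effect on the results is small. On the assumed distributions, and with every site using mmol/L, eligibility for rescue rises by about 0.5 percentage points in Weeks 12 to 26 and 0.9 points in Weeks 26 to 78. The rescue cut-offs are the same in both arms and randomization is stratified by country, so material bias in the HbA1c comparison is unlikely. The 200/11 pair applies only from Week 26 on. EAS1, which serves the treatment regimen estimand, keeps data regardless of rescue and so is not cut. Sample size and power are unaffected. The arithmetic is certain; the size depends on the assumed glucose distribution and on a use of mmol/L that the documents do not establish.

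**What to change.** - Reconcile the 240/13 and 200/11 pairs in Protocol 6.8.1.
- State one governing unit for all FBG-based rescue, loading-dose and titration decisions, and for the 6.8.5.1 rule, with the other unit for information only. Correcting the decimals alone cannot make every reading give the same action in both units.
- Align the conversion of 140 mg/dL between Protocol 10.8 and SAP 6.6.1.
- If participants have already been treated, record which unit the portal and sites applied.

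The cut-offs themselves are for the sponsor to set. The cost is protocol and SAP wording, with a check of the dosing tables and portal settings; no new data are needed.
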